#### 3.2 Study Design

This is a prospective, multicenter, open-label study assessing RBX2660 as an adjunct to antibiotics for the treatment of recurrent CDI. Up to approximately 150 subjects will be enrolled in this study. Efficacy of RBX2660, measured by the recurrence-free rate of CDI diarrhea without the need for retreatment with *C. difficile* anti-infective therapy or fecal transplant through 56 days after completion of study treatment with RBX2660, will be evaluated by comparing the recurrence-free rate observed in the study population to the recurrence-free rate identified from antibiotic-treated historical controls. Subjects who meet all inclusion and exclusion criteria, including having a positive *C. difficile* test within 60 days prior to enrollment and experiencing either a) at least two recurrences after a primary episode and have completed at least two rounds of standard-of-care oral antibiotic therapy or b) have had at least two episodes of severe CDI resulting in hospitalization prior to enrollment, will receive treatment with RBX2660. One study treatment consists of two RBX2660 enemas administered  $7 \pm 2$  days apart (no antibiotics between doses); the second enema may be administered sooner if CDI diarrhea reoccurs in less than 7 days. Subjects will already be taking or will start a course of antibiotics to control recurrent CDI diarrhea at the time of enrollment, [REDACTED]

[REDACTED] An in-office follow-up visit will occur at 8 weeks after completing study treatment for the assessment of AEs, efficacy, collection of the Subject Diary, and blood tests. Telephone assessments for adverse events including SAEs and the new onset of chronic diseases and CDI symptoms will occur at weeks 1, 2, 3, and 4 and at 3, 6, and 12 months after completing study treatment. Assessment of serious adverse events and the new onset of chronic diseases will occur via phone call at 24 months after completing study treatment. Subjects will

keep a detailed Subject Diary to allow for assessment of solicited adverse events (see Section 7.1.3) from the date of enrollment to 1 week after completing study treatment. Treatment failures (as determined by the site investigator at the time of CDI recurrence) are eligible to receive another therapy deemed most appropriate by their study investigator; see “Management of Treatment Failures,” below.

[REDACTED]

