4 STUDY DESIGN

4.1 General Design

This is a prospective, multicenter, open-label study assessing the efficacy and safety of RBX2660 as an adjunct to antibiotics for the treatment of recurrent CDI. Up to approximately 150 subjects will be enrolled in this study and receive RBX2260. Approximately 100 historical controls will be chosen from a retrospective chart review of patients treated with antibiotics for recurrent CDI who match key inclusion/exclusion criteria from the study.

Subjects who meet all inclusion and exclusion criteria, including having a positive *C. difficile* test within 60 days prior to enrollment and experiencing either a) at least two recurrences after a primary episode (diagnosis must include at least one positive *C. difficile* test on record within 60 days prior to enrollment) and have completed at least two rounds of standard-of-care oral antibiotic therapy or b) have had at least two episodes of severe CDI resulting in hospitalization prior to enrollment, will receive open-label treatment with RBX2660. One study treatment consists of two RBX2660 enemas administered 7 ± 2 days apart; the second enema may be administered sooner if CDI diarrhea reoccurs in less than 7 days. Subjects will already be taking or will start a course of antibiotics to control recurrent CDI diarrhea at the time of enrollment, [REDACTED]

[REDACTED] An in-office follow-up visit will occur at 8 weeks after completing study treatment for the assessment of AEs, efficacy, collection of the Subject Diary, and blood tests. Telephone assessments for AEs including serious adverse events (SAEs) and the new onset of chronic diseases and CDI symptoms will occur at weeks 1, 2, 3, and 4 and at 3, 6, and 12 months after completing study treatment. Assessment of serious adverse events and the new onset of chronic diseases will occur via phone call at 24 months after completing study treatment. Subjects will keep a detailed Subject Diary to assess for solicited adverse events from the date of enrollment to one week after completing study treatment (second enema). Treatment

failures (as determined by the site investigator at the time of CDI recurrence) are eligible to receive another therapy deemed most appropriate by their study investigator.

[REDACTED]

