4.7 Treatment Arms

The open-label study consists of a single prospective treatment arm and historical control group, as described below.

- One treatment with RBX2660: one treatment consists of two enemas of RBX2660 administered 7 ± 2 days apart (the second enema may be administered sooner if CDI diarrhea reoccurs in less than 7 days). [REDACTED]
- Historical control group chosen from a retrospective chart review.

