6.3 Analysis Populations

Enrolled Population: includes all subjects enrolled into the study, including subjects in the historical control arm.

Safety Population: includes all subjects enrolled into the study who received any study treatment with RBX2660; this does not include subjects in the historical control arm.

Full Analysis Set (FAS) Population: includes the Safety Population and subjects in the historical control arm.

Evaluable Population: includes the FAS subjects who were evaluable for treatment outcome (e.g., exclude subjects that discontinued from the study prior to determination of treatment failure and were not followed for at least 56 days (day 49 – 63) after the last treatment date).

Per Protocol Population: includes subjects from the Evaluable Population, excluding:

- Subjects from the Safety Population that did not complete 2 enemas

- Subjects that received fecal microbiota transplant before the 8-week follow-up and lacked a documented recurrence of CDI (Treatment Failure eCRF)
- Violations to the inclusion or exclusion criteria, including protocol definition of recurrent CDI two hospitalizations for CDI or 3 recurrent CDI events
- Received prohibited medication during the 8-week follow-up period

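### The Per Protocol set in SAP 6.3 does not look at the days between the two enemas, so a subject given antibiotics between doses stays in it

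*SAP*

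**What the plan says.** **Dosing.** Protocol 3.2, and the Study Design row of the synopsis, set the two enemas 7 ± 2 "days apart (no antibiotics between doses); the second enema may be administered sooner if CDI diarrhea reoccurs in less than 7 days". SAP 4.1 restates this as "One study treatment consists of two RBX2660 enemas administered 7 ± 2 days apart; the second enema may be administered sooner" and goes on to the diarrhea condition. The antibiotic condition does not appear at that point in its sentence.

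**Per Protocol set.** SAP 6.3 takes the Evaluable Population and removes four groups:

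1. "Subjects from the Safety Population that did not complete 2 enemas"
2. subjects who had a fecal transplant before the 8-week follow-up with no documented recurrence
3. "Violations to the inclusion or exclusion criteria, including protocol definition of recurrent CDI two hospitalizations for CDI or 3 recurrent CDI events"
4. "Received prohibited medication during the 8-week follow-up period"

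**Start of the 8 weeks.** SAP 4.1 states: "An in-office follow-up visit will occur at 8 weeks after completing study treatment for the assessment of AEs". Protocol 3.2 and 6.8 use the same anchor, and the Evaluable definition in SAP 6.3 counts from the last treatment date.

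**Use.** SAP 8.7.1 runs the primary efficacy analysis on the Evaluable Population and repeats it on the Full Analysis Set and the Per Protocol set.

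**The concern.** A per-protocol analysis is useful only if its members received the treatment as the protocol defines it. Here the definition has three visible parts: two enemas, an interval between them, and no antibiotics in that interval. The analysis set enforces the first part only. An antibiotic active against *C. difficile*, taken between doses, acts on the disease under study. A subject who received one no longer shows what the two enemas do on their own.

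The study is open-label, has no randomization and uses a historical control, so its supportive analyses carry more weight than usual.

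The medication exclusion has a second gap: it does not end when the subject fails. The failure definition includes a need for retreatment, and failures are then treated as the investigator sees fit. The fecal transplant exclusion in the same list allows for this by sparing documented recurrences. The medication exclusion does not.

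**Working it through.** The plan states no figure on this point, and the sample-size assumptions are redacted, so there is nothing to reproduce. The check sets each part of the dosing rule against the four exclusions.

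| Part of the rule (Protocol 3.2) | Covered by an exclusion in SAP 6.3? |
|---|---|
| Two enemas given | Yes, exclusion 1 |
| Second enema on days 5 to 9 (7 − 2 = 5, 7 + 2 = 9), or sooner if diarrhea returns | No; exclusion 1 counts enemas and does not look at dates |
| No antibiotics between enemas | No; see the steps below |

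**Exclusion 4 (medication).** Its period is the 8-week follow-up. Every visible anchor starts the 8 weeks at the last enema. The interval between doses ends at the last enema, so it lies wholly before the period checked.

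**Exclusion 3 (eligibility).** Protocol 6.5 and the schedule in SAP 6.1 confirm eligibility at Visits 1 and 2, before the interval begins. The visible antibiotic criterion in Protocol 4.2 concerns continuous therapy for a condition other than CDI. It does not reach a short course, or a CDI antibiotic, taken between doses.

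**Exclusion 2 (transplant).** It concerns fecal transplant only.

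**Outcome definition.** Failure is counted from the end of treatment (Protocol 3.6) or the last assigned enema (SAP 4.1.4). Success must hold through 56 days after that point, but no start is given. An antibiotic between doses is therefore neither excluded nor clearly scored as a failure.

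**Effect on the rate.** If a fraction *f* of the RBX2660 Per Protocol subjects broke the rule, and their success rate differs from that of the rest by *d*, the observed rate moves by *f* × *d*. The documents give neither quantity. For scale only, assume 140 two-enema subjects, 10 of them rule-breakers, and 78% success in the other 130 (130 × 0.78 = 101.4):

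- all 10 succeed: (101.4 + 10)/140 = 79.6%, a shift of +1.6 points
- none succeed: 101.4/140 = 72.4%, a shift of −5.6 points

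These inputs are invented. The example shows only that the direction is open.

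**The case against.** **Redaction.** No definition of prohibited medication is visible. The text of Protocol 5.6 (Concomitant Therapy) and SAP 8.2 (Protocol Deviations) cannot be seen, and part of the antibiotic inclusion criterion is blacked out. Hidden text could restrict antibiotics between doses, and exclusion 3 might then reach some cases. This stands as a caution. It does not remove the point, because the Per Protocol list itself is unredacted and limits the medication check to the follow-up.

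**SAP dosing text.** A reader might infer that the SAP abandoned the antibiotic condition altogether. The documents do not show that. The dosing sentence in SAP 4.7 runs straight into a redaction, and so does the later antibiotic sentence in SAP 4.1. Several short definitions in the protocol (2.1 and 5.1, for example) also leave the condition out. What can be shown is a difference at the matching point of SAP 4.1.

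**Retreated failures.** A reader might infer that the medication exclusion would remove every retreated failure and drive the success rate towards 100%. That needs retreatment drugs to be on a list nobody can see. Protocol 3.7 and SAP 4.1.5 direct that failures be treated, and treatment the plan directs is not naturally prohibited. The transplant exclusion also suggests that documented failures were meant to stay. Only the missing stop point is established.

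**Bias in favor of RBX2660.** A reader might infer that antibiotics between doses inflate the result. Because the success definition fixes no start, needing such an antibiotic may already count against success. The direction is not known.

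**Off-interval enemas.** Whether a second enema just outside the interval matters enough for exclusion is a judgement. One brought forward for returning diarrhea is allowed and is no deviation. Both points stand, so the request is for a stated rule and not for automatic exclusion.

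**Conclusion.** The point holds as a gap in a supportive analysis set. On the visible text, a subject given antibiotics between the enemas satisfies every Per Protocol condition while departing from the treatment described in Protocol 3.2. The same is true of a second enema after day 9, or before day 5 without returning diarrhea, although its importance is for the sponsor to settle.

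The missing stop at failure is an inconsistency with the neighboring exclusion. Its consequence depends on a hidden list, so no size can be attached to it.

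The conclusion assumes that the 8-week follow-up starts at the last enema, as all visible anchors say, and that no redacted passage widens the medication check. The primary analysis does not use this set, so its result does not change. Nothing in the documents suggests that such departures are common.

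**What to change.** In SAP 6.3:

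- Apply the prohibited-medication exclusion from the first enema until day 56 after the last enema or the determination of treatment failure, whichever is earlier. Historical controls, who have no enemas, keep their existing window.
- Count antibiotics taken between the enemas in that exclusion, in line with the protocol's dosing definition.
- State before analysis whether a second enema outside the protocol's interval, other than one brought forward as Protocol 3.2 allows, is an important deviation that removes a subject from the set.

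Reconcile the dosing description in SAP 4.1 with Protocol 3.2. Which wording is correct is for the sponsor to settle.

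The cost is SAP wording. Concomitant medications are recorded at every visit and call in the SAP schedule, and the enemas are the scheduled procedures of Visits 2 and 3, so no new data are needed. The downside is a slightly smaller Per Protocol set.

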6.4 Safety Variables

Safety variables to be evaluated in the study include:

- Adverse events (AEs)
- Serious adverse events (SAEs)
- Solicited AEs
- Frequency of major complications of recurrent CDI including death, septic shock, toxic megacolon, colonic perforation, emergency colectomy, or ICU admission.

[REDACTED]

[REDACTED]

[REDACTED]

[REDACTED]

[REDACTED]

[REDACTED]

[REDACTED]

[REDACTED]

[REDACTED]

[REDACTED]

[REDACTED]

6.4.2 Adverse Events

An adverse event (AE) is any untoward medical occurrence associated with the use of RBX2660, whether or not the event is considered product-related. Pre-existing conditions that worsen in frequency, intensity or character of the condition during study participation will be recorded as an AE. Adverse events will be recorded for each subject from the day of enrollment through the 12-month phone call. Serious adverse events (SAEs) and the new onset of chronic diseases will be recorded for each subject from the day of enrollment through the duration of the study.

6.4.2.1 Adverse Event Dictionary

Adverse events and SAEs will be classified by the Medical Dictionary for Regulatory Activities (MedDRA) [REDACTED]

6.4.2.2 Adverse Event Severity

The severity of AEs will be graded as mild, moderate, severe, or potentially life-threatening. The severity grade of events for which the investigator does not record severity will be categorized as “Unknown” for tabular summaries and data listings, and will be considered the least severe for the purposes of sorting for data presentation. For summaries by severity grade, if a subject has multiple events occurring in the same SOC or PT, then the most severe event will be selected.

6.4.2.3 Relationship of Adverse Events to Study Treatment

Causal relationship of an AE to RBX2660, the enema procedure, *C. difficile* disease, and/or a pre-existing condition will be classified by the investigator as definite, probable, possible, or unrelated. Related events will include AEs that are classified as definitely, probably or possibly related. Events for which the investigator does not record causal relationship will be considered "Related" for tabular summaries and data listings.

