8.6.1 Adverse Events

A summary of adverse events, TEAEs, non-serious TEAEs, and serious TEAEs will be summarized using counts of the number of events and frequencies (counts and percentages) of the number of subjects in the Full Analysis Set. The frequency of each preferred term (PT) within the primary system organ class (SOC) as well as overall primary SOC frequency will be presented. A subject with multiple events coded to the same PT within a primary SOC will be counted only once for the PT within the primary SOC. Likewise, a subject with multiple events coded to the same SOC will be counted only once within the SOC. Adverse events and serious adverse events will also be summarized by onset timepoint by system organ class (SOC) and preferred term (PT): [REDACTED]

[REDACTED]

[REDACTED] Adverse events will be counted in the interval in [REDACTED]

which the start date of the event occurs. For subjects with multiple instances of the same event, the events will be counted once within each interval that the event starts.

An overall summary of AEs will present the frequency of all TEAEs, serious TEAEs, and TEAEs leading to death for the Full Analysis Set, as well as the frequency of the following for the RBX2660 treatment group:

- TEAEs related to RBX2660
- TEAEs related to enema procedure
- TEAEs related to *C. difficile* disease
- TEAEs related to a pre-existing condition
- Serious TEAEs related to RBX2660
- Serious TEAEs related to the enema procedure
- Serious TEAEs related to *C. difficile* disease
- Serious TEAEs related to a pre-existing condition.

Frequency of occurrence and number and percentage of subjects experiencing an event will be presented by SOC and PT using the Safety Population for the following:

- TEAEs by maximum severity
- TEAEs by relatedness to RBX2660
- TEAEs by relatedness to *C. difficile* disease
- TEAEs by relatedness to enema procedure
- TEAEs by relatedness to pre-existing condition
- Serious TEAEs
- Serious TEAEs by maximum severity
- Serious TEAEs by relatedness to RBX2660
- Serious TEAEs by relatedness to *C. difficile* disease
- Serious TEAEs by relatedness to enema procedure
- Serious TEAEs by relatedness to pre-existing condition

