For the summary of AEs by maximum severity, if a subject has multiple events occurring in the same SOC or same PT, then the event with the highest severity will be counted. For AEs reported by causality, if a subject has multiple events occurring in the same SOC or same PT, the event with the highest association will be summarized.

A summary of TEAE and serious TEAE characteristics (severity, relatedness to RBX2660, relatedness to *C. difficile* disease, relatedness to enema procedure, and relatedness to pre-existing condition by outcome) will be presented for the Safety Population.

A summary of TEAE and serious TEAE characteristics (severity, relatedness to RBX2660, relatedness to *C. difficile* disease, relatedness to enema procedure, and relatedness to pre-existing condition by outcome) by SOC will also be presented for the Safety Population.

For data presentation, SOC will be ordered alphabetically, with PT sorted by decreasing total frequency. No inferential statistics will be provided for the AE data.

Subject listings will be presented for all AEs and for SAEs.

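### The blank-equals-'Related' default also fills the disease and pre-existing-condition tables, and the rank given to ungraded events can understate maximum severity

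*SAP*

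**What the plan says.** **Causality.** SAP 6.4.2.3 lists RBX2660, the enema procedure, *C. difficile* disease "and/or a pre-existing condition will be classified by the investigator as definite, probable, possible, or unrelated". The causes are joined so that one event can carry several. The grouping rule is "Related events will include AEs that are classified as definitely, probably or possibly related". The default for a blank is "Events for which the investigator does not record causal relationship will be considered" 'Related' in tables and listings. It is not tied to any one of the four causes.

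SAP 8.6.1 then plans one table per cause, starting with "TEAEs by relatedness to RBX2660" and repeated for the disease, the procedure and a pre-existing condition, and plans the same four for serious TEAEs. When a subject has several events in one SOC or PT, "the event with the highest association will be summarized".

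**Severity.** SAP 6.4.2.2 labels a missing grade 'Unknown' and adds that it "will be considered the least severe for the purposes of sorting for data presentation". The next sentence of that section has the most severe event chosen within a SOC or PT. SAP 8.6.1 repeats this for the maximum-severity tables: "then the event with the highest severity will be counted". The visible text gives 'Unknown' no other rank.

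**The concern.** A default for missing safety data should be cautious in the direction that matters for each field. Counting a blank as related is cautious for RBX2660 and the enema procedure. For the disease and for a pre-existing condition it is not, because those attributions describe another explanation for the event. Protocol 7.1.7 treats them this way: investigators are told to weigh other explanations, including the CDI itself, and 'unrelated' is defined by an underlying or concurrent illness or another therapy.

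On severity, a rule that puts a missing grade below mild lets an ungraded event disappear from a maximum-severity table whenever the same subject has any graded event in the same SOC or PT.

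These tables matter more here than in a randomised trial. There is no concurrent control, Protocol Appendix 1 (A1) expects the historical-control safety data to be scant and does not use them for comparison, and SAP 8.6.1 plans no inferential statistics on adverse events. The descriptive tables are therefore the main safety output, and missing-value rules feed straight into them.

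**Working it through.** The plan gives no figure to reproduce, so the check applies each rule to every possible case.

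**1. Causality**

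Inputs: each field can be unrelated, possible, probable, definite or blank (SAP 6.4.2.3). Take two fields, RBX2660 and *C. difficile* disease. That gives 5 × 5 = 25 combinations.

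- SAP rule: an event is related to a cause if that field is possible, probable, definite or blank.
- Comparison: the same, but with a blank not counted as related.

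Results:

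- RBX2660-related status is lowered by the SAP rule in 0 of 25 combinations. It is raised in 1 × 5 = 5, those where the RBX2660 field is blank.
- Disease-related status is likewise raised in 5 × 1 = 5 combinations, those where the disease field is blank. In each, the disease table gains an entry that no investigator made.
- The disease default changes RBX2660-related status in 0 of 25, because each table depends only on its own field.
- In one of those 5 combinations RBX2660 is recorded as unrelated and the disease field is blank. There the rule supplies an alternative cause for an event already judged not due to the product.

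The pre-existing-condition field behaves in the same way. At subject level, the highest-association rule lets a blank counted as 'Related' outrank a recorded 'unrelated' for another event in the same SOC or PT.

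If the default is limited to RBX2660 and the enema procedure, RBX2660-related status changes in 0 of 25 combinations, and disease-related status falls back in the 5 with a blank disease field.

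**2. Severity**

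Inputs: four grades plus 'Unknown' (SAP 6.4.2.2). Take a subject with one graded and one ungraded event in the same SOC or PT, with 'Unknown' ranked lowest.

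| Graded event | Tabulated as | True grades of the ungraded event that stay hidden |
|---|---|---|
| Mild | Mild | Moderate, severe, potentially life-threatening |
| Moderate | Moderate | Severe, potentially life-threatening |
| Severe | Severe | Potentially life-threatening |
| Potentially life-threatening | Potentially life-threatening | None |

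The recorded grade is kept in all four pairs, so any error is downward. A subject with only ungraded events is shown as 'Unknown', not as mild.

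With 'Unknown' ranked highest instead, all four pairs would be tabulated as 'Unknown' and every recorded grade would be lost. Re-ranking is therefore not a clean remedy.

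**3. Size**

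Each blank adds at most one event to the affected alternative-cause table. Each ungraded event hides at most one subject's higher grade in a SOC or PT row. The visible documents give neither an expected number of adverse events nor a rate of blank fields, so no total follows.

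**The case against.** A reader might infer that both rules favour the product. The documents do not support that. For RBX2660 and the enema procedure the default works against the product, and because the causes are not exclusive and are tabulated separately, an extra disease-related entry removes nothing from a product-related table. If no causal field at all was completed, the event counts against the product too. That part of the objection stands in full.

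A reader might also infer that ungraded events are treated as mild. They are not: they have their own category, and in a mild-plus-ungraded pair the mild grade is a recorded one. The low rank is stated for sorting and presentation, so its use in choosing the maximum is an inference. It is a fair one, because the selection rule is the very next sentence and the visible text offers no other rank, but it is not stated. Nor do ungraded events vanish from the report: SAP 8.6.1 also plans event counts, summaries of TEAE characteristics and listings.

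Blanks should be uncommon. Protocol 7.1.6 and 7.1.7 require the investigator to grade severity and to assess causality for all events, 7.1.8 has a Medical Monitor adjudicate SAEs and events of interest, and 9.8 requires the investigator to review and sign the eCRFs. This limits the size but does not settle how remaining blanks are tabulated. Parts of SAP section 7 and the method reference in SAP 8.6 are blacked out, so a further rule may exist there.

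**Conclusion.** The point holds for the two alternative-cause fields and, conditionally, for severity. As SAP 6.4.2.3 is worded, blanks inflate the tables of events related to *C. difficile* disease and to a pre-existing condition; this rests on reading the default field by field, which the unrestricted wording allows. Product- and procedure-related counts are not lowered. If the least-severe rank carries into the choice of maximum grade, the maximum-severity tables can be understated but not overstated. The size cannot be computed from the documents. The effect is on descriptive output only and is probably small. It is worth correcting because the correction is cheap and cannot reduce any product-related count.

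**What to change.** - **SAP 6.4.2.3:** limit the 'Related' default to RBX2660 and the enema procedure. Show blanks for *C. difficile* disease and for a pre-existing condition as 'not recorded', and report the number of blanks for each field.
- **SAP 6.4.2.2 and 8.6.1:** keep the highest recorded grade as the tabulated maximum, and add to each SOC and PT row of the maximum-severity tables the number of subjects with any ungraded event.

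Counting ungraded events as severe is not advised: it could overwrite a recorded moderate grade, and it sits badly with Protocol 8.5, which plans no imputation for safety. The changes above impute nothing new.

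Cost: a few sentences in the SAP and slightly larger tables.
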